9.2.3 Subject demographics

For demographic data of the subject, date of birth (or age at enrollment if date cannot be provided) and sex will be checked. Also, the following items concerning the primary disease of colorectal cancer will be examined.

(1) Information on primary organ

- Solitary/Multiple
- Primary tumor site (cecum, ascending colon, transverse colon, descending colon, sigmoid colon, rectosigmoid, rectum)

(2) Information on metastasis

- Number of organs with metastasis (0, 1, ≥ 2)*

*: Does not include primary tumor/regional lymph node, other lymph nodes in several sites will be counted as “1 organ”. For example, even if it is observed in cervical lymph node and thoracic lymph node, it will be counted as 1 organ.

- Organs with metastasis (liver, lung, peritoneum, lymph node*, bone, adrenal gland, skin, and others**)

*: Does not include regional lymph node, other lymph nodes in several sites will be counted as “1 organ”. For example, even if it is observed in cervical lymph node and thoracic lymph node, it will be counted as 1 organ.

**: Name of organ to be recorded in CRF

(3) History of treatment

- History of surgery in primary tumor site/palliative metastasis site and history of colostomy /bypass surgery

- Subjects with history, the date of surgery
However, endoscopic surgery, which is not considered a history of surgery, should not be entered into the CRF.

- History of radiotherapy (radical irradiation)

- Subjects with history, the date of final dose
However, irradiation for pain relief (palliative irradiation) in the bone metastasis site, which is not considered as radiotherapy, should not be entered into the CRF.

- Treatment history for subjects with unresectable lesions

- Description of first-, second-, and third-line treatment (FOLFOX, FOLFOX + anti-angiogenic agent (e.g., bevacizumab); CapeOX, CapeOX + anti-angiogenic agent (e.g., bevacizumab); FOLFIRI, FOLFIRI + anti-angiogenic agent (e.g., bevacizumab); IRIS, IRIS + anti-angiogenic agent (e.g., bevacizumab); IRI, IRI + anti-angiogenic agent (e.g., bevacizumab); FOLFOXIRI, FOLFOXIRI + anti-angiogenic agent (e.g., bevacizumab); SOX, SOX + anti-angiogenic agent (e.g.,

CONFIDENTIAL

bevacizumab); SOX, SOX + anti-angiogenic agent (e.g., bevacizumab); other), date of initiation of first-line treatment

- History of preoperative and/or postoperative adjuvant chemotherapy

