7.2.2 Analysis of demographic and other baseline characteristics

7.2.2.1 Demographic and other baseline characteristics

The following analyses will be performed on “all enrolled subjects,” the “full analysis set,” and the “safety analysis set”:

(1) Discrete data

A frequency distribution will be tabulated for discrete data, and the percentage (%) will be indicated with the analysis set as a denominator. Tabulation items are as follows:

- Age (≥ 20 to < 30 years, ≥ 30 to < 40 years, ≥ 40 to < 50 years, ≥ 50 to < 60 years, ≥ 60 to < 70 years, ≥ 70 to < 75 years; ≥ 20 to < 65 years, ≥ 65 to < 75 years), sex, information on primary organ tumor (solitary, multiple), primary tumor location [colon (cecum, ascending colon, transverse colon, descending colon, sigmoid colon), rectum (rectosigmoid, rectum)], [right side, left side], information on metastasis (number of organs with metastasis) (0, 1, ≥ 2), organs with metastasis (liver, lung, peritoneum, lymph node, bone, adrenal gland, skin, and others), ECOG Performance status (P.S.) [before treatment on Day 1 of Course 1 (0, 1)], resection of primary tumor (yes, no), adjuvant chemotherapy (yes, no), number of previous treatments (1, 2, 3), complications (absence, presence).

(2) Continuous data

Summary statistics (number of cases, the mean, standard deviation, minimum, maximum, quartiles) will be calculated for continuous data.

- Age (years), height (cm), body weight (kg) (at enrollment), BMI (kg/m^2) (at enrollment), period from the start date of first-line treatment to the date of enrollment (months) (One month is considered as 28 days in calculations).

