7.2.4.3 Subgroup analysis of efficacy

1) Subgroup analysis on the following items will be performed for each background factor described below. The same analysis method will be used as in Sections 7.2.4.1 and 7.2.4.2. Using all background factors as explanatory variables, multivariate analysis will be performed using the Cox proportional hazard model for PFS, OS, and TIF. Similarly, using all background factors as explanatory variables, logistic regression analysis will be performed for PFS rate and DCR.

7.2.4.3.1.1 PFS rate

7.2.4.3.1.2 PFS

7.2.4.3.1.3 OS

7.2.4.3.1.4 RR

7.2.4.3.1.5 DCR

7.2.4.3.1.6 TTF

Background factors:

Age (≥ 20 years < 65 years, ≥ 65 years < 75 years), sex, ECOG Performance status (P.S.) [before dosing on Day 1 of Course 1 (0, 1)], information on primary tumor location [right, left], adjuvant chemotherapy (yes, no), resection of primary lesion (yes, no), number of days since the start of first-line treatment (< 600 days, ≥ 600 days)

2) A landmark analysis for PFS, OS, and TIF will be performed for each landmark point after enrollment. Patients developing applicable events by the landmark point after enrollment and those who have been discontinued will be excluded from the analysis. The same analysis method will be used as in Section 7.2.4.2.

7.2.4.3.2.1 PFS

7.2.4.3.2.2 OS

7.2.4.3.2.3 TTF

Factor	Landmark point	Category
Skin Toxicity,	Week 6	$\leq G1, \geq G2$
Skin Toxicityr	Week 10	$\leq G1, \geq G2$

Factor	Landmark point	Category
Stomatitis	Week 6	$\leq G1, \geq G2$
Stomatitis	Week 10	$\leq G1, \geq G2$
Neutropenia	Week 6	$\leq G0, \geq G1$
Neutropenia	Week 6	$\leq G2, \geq G3$
Early Tumor Shrinkage (ETS)*	Week 8	Yes, No

*ETS refers to the case of tumor shrinkage by at least 20% within 8 weeks after enrollment.

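### The exploratory multivariable models use age and time since first-line treatment only as two-level factors, although both are collected as continuous values

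*SAP*

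**What the plan says.** SAP version 4.0, section 7.2.4.3 part 1), plans subgroup analyses by a list of background factors and then models built on the same list. For the time-to-event endpoints: "Using all background factors as explanatory variables, multivariate analysis will be performed using the Cox proportional hazard model for PFS, OS, and TIF". With the same factors, "logistic regression analysis will be performed for PFS rate and DCR".

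The list has seven factors, each with two levels: age, sex, ECOG performance status, primary tumor side, adjuvant chemotherapy, resection of the primary lesion, and time since first-line treatment. Two of them are continuous by nature:

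- "Age (≥ 20 years < 65 years, ≥ 65 years < 75 years"
- "number of days since the start of first-line treatment (< 600 days, ≥ 600 days"

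No section says that either enters a model in any other form. Both exist as continuous data. Protocol 9.2.3 says "date of birth (or age at enrollment if date cannot be provided) and sex will be checked", and it also collects the date on which first-line treatment began. SAP 7.2.2.1 summarises age in years and the "period from the start date of first-line treatment to the date of enrollment (months) (One month is considered as 28 days in calculations" as continuous variables.

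The 65-year cut already stands in the baseline tables of SAP version 1.0. The 600-day cut appears only in version 4.0 (July 10, 2018). Version 3.0 planned efficacy subgroups by primary lesion side alone. No reason is given for 600 days.

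**The concern.** Subgroup tables need categories; a regression model does not. A two-level term and a single linear term each use one degree of freedom, so the split saves nothing. It treats a subject aged 64 and one aged 65 as different, and subjects aged 65 and 74 as the same. If the effect changes steadily with age or time, the variation within each level is discarded.

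What is at stake is the chance of detecting a real prognostic effect of these two factors, in models that have at most about 52 subjects and seven factors.

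**Working it through.** **Size of the analysis set.** Protocol 6.2.2.2 states 47 subjects for 29% against 48%, one-sided 5%, power 80%. The exact binomial test reproduces this: with n = 47 the null is rejected at 20 or more successes, with exact alpha 0.0327 and power 0.814, and power stays at or above 80% from n = 47 upward. Adding 10% gives 47 × 1.10 = 51.7, so 52. The full analysis set drops untreated and ineligible subjects, so it holds at most about 52. The documents state no figure for information lost by splitting.

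**Information kept by a split.** If a covariate X acts linearly on the model scale, the share of information kept by the indicator of X ≥ c is the squared correlation between the two. For a normal X with share p on one side of the cut this is φ(z_p)² / [p(1 − p)]:

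- p = 0.5: 0.3989² / 0.25 = 0.637, a loss of 36.3%; 52 × 0.637 = 33.1 effective subjects for that factor
- p = 0.3: 0.576, a loss of 42.4%; 29.9 effective subjects
- p = 0.2: 0.2800² / 0.16 = 0.490, a loss of 51.0%; 25.5 effective subjects
- p = 0.1: 0.342, a loss of 65.8%; 17.8 effective subjects

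**Other shapes.** All distributions here are assumptions.

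- Uniform X keeps 3p(1 − p): a loss of 25% at 50/50 and 52% at 80/20.
- Age normal with mean 58–68 and SD 8–12, truncated to 20–75 and cut at 65: a loss of about 33% to 56%.
- Days lognormal with median 450–900 and log-SD 0.4–0.8, cut at 600: about 36% to 57% if the effect is linear in log(days), and about 38% to 77% if it is linear in days.
- A true step exactly at the cut: no loss from the split. The squared correlation is symmetric, so the linear term would then be the one that loses.

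**What this means for power.** The documents give neither an event count nor a covariate effect, so both are assumed. With D events and a hazard ratio of 1.5 per SD, two-sided 5% power is about Φ(√(D × share kept) × ln 1.5 − 1.96). For D = 45, √45 × 0.4055 = 2.720:

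- continuous term: Φ(2.720 − 1.96) = 0.776
- 50/50 split: Φ(2.720 × √0.637 − 1.96) = 0.583
- 80/20 split: Φ(2.720 × √0.490 − 1.96) = 0.478

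For D = 40 the three values are 0.727, 0.534 and 0.434; for D = 52 they are 0.832, 0.645 and 0.534. Simulated Cox fits (n = 52, about 46 events, six independent binary covariates, the same hazard ratio, 1,000 to 1,200 fits per run) agree. Across runs, power was 69–74% with a continuous term and 50–54% with a median split. At 30/70 it was 68–71% against 44–52%. Only Cox models of this kind were simulated, not the logistic models.

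**The case against.** The strongest reply has four parts.

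- The SAP does not spell out the model coding; the levels stand in a list that also serves the subgroup tables. This is true, but the list is the only definition of the factors and the models use that list, so two-level coding is the natural reading.
- Fixed categories let the models match the tables, and the 65-year cut dates from SAP version 1.0. Both are fair reasons to keep the categories for the tables.
- No trial conclusion depends on these models, and sparse data limits them far more than coding does. At the assumed 48%, 0.48 × 52 ≈ 25 successes, or about 3.6 per factor in the logistic model for the PFS rate. This stands, and recoding two terms does not cure it.
- A percentage loss is not a property of this trial. This stands as well. It needs a distribution, an effect shape and a split that the documents do not give.

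A reader might go on to infer that the split leaves material residual confounding in the other five estimates. The documents give no correlations to support that. With a correlated binary factor that has no true effect, in the simulated setting above, its log hazard ratio shifted by about 0.09–0.10 at latent correlation 0.3 (standard error about 0.35) and by 0.12–0.16 at 0.5 (standard error about 0.36). Its false-positive rate rose by 0.6 to 2.3 percentage points. There is also no treatment contrast to confound in a single-arm study.

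A reader might also infer that the 600-day cut was chosen from the data, because version 4.0 is dated after the planned study end of March 2018. The documents do not say what had been seen by then, so this cannot be concluded.

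**Conclusion.** The point holds as a minor, inexpensive improvement to exploratory models. As written, SAP 7.2.4.3 part 1) reduces two continuous variables to two levels in five multivariable models, with no saving in degrees of freedom.

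If a factor is roughly normal with a linear effect on the model scale, the information lost on it is about 36% at an even split and about 51% at 80/20. At a hazard ratio of 1.5 per SD and 45 events, that is a fall in power of about 19 points (0.776 to 0.583) or 30 points (0.776 to 0.478). A single range for both variables should not be read as a fact about this trial: the loss runs from zero (a step at the cut) through about 25% (uniform, cut at the median) to well above 50% for skewed days.

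The primary binomial test, the secondary Kaplan-Meier estimates and the response rates are untouched.

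**What to change.** In SAP 7.2.4.3 part 1), keep the two-level categories for the subgroup tables. Add a sentence that, in the Cox and logistic models, age in years and the logarithm of days from the start of first-line treatment to enrollment each enter as one linear term. Report hazard or odds ratios per 10 years of age and per doubling of time. Fix the log form now; a rule to transform only if the data look skewed would let the model depend on the data. Give a reason for 600 days if that cut stays in the tables.

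The cost is SAP wording only: no new data and no extra degree of freedom. The downsides are that a linear (for time, log-linear) shape is assumed, which a residual plot can check as a description without changing the model, and that the model terms no longer match the subgroup categories.

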As increased anti-tumor effect can be expected by using TAS-102 in combination with panitumumab treatment which is the standard treatment for patients with unresectable, advanced/recurrent colorectal cancer, the PFS rate at 6 months in this study was assumed to be 48% and this was set as the expected value for the panitumumab treatment in combination with TAS-102 therapy in patients with RAS wild-type unresectable, advanced/recurrent colorectal cancer. *Also, for the threshold where* further development for panitumumab treatment in combination with TAS-102 may be considered not necessary, it was assumed to be 29% from the CI lower limit of the PFS rate at 6 months in the ASPECCT study.¹⁷⁾

For the main analysis, based on the observed PFS rate at 6 months from start of treatment, binomial test will be conducted on the null hypothesis “the true PFS rate at 6 months from start of treatment will be not more than the PFS threshold rate where value is determined invalid”. With the PFS threshold rate at 29%, PFS expected rate at 48% at 6 months from start of treatment, and one-sided significant level at 5%, power at 80%, the necessary number of subjects will be 47. Taking into consideration of ineligible or discontinued subjects at approximately 10%, the target number of subjects was set to 52 (including subjects that received RD in the phase I part).

6.3 Discontinuation of entire clinical study or discontinuation of clinical study at a study site

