
The following analysis will be performed on the “full analysis set.”

PFS rate at 6 months is calculated by counting of subjects with progression, without progression, and unconfirmed at 6 months. Based on the observed PFS rate at 6 months from the day of enrollment, binomial test will be conducted on the null hypothesis “value will be determined invalid at PFS rate $\leq 29\%$.” Significant level will be 2.5% (one-sided) in the main analysis. For interval estimation, accurate 90% confidence interval (two-sided) based on binomial distribution will be used.

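### The seven-factor logistic models for PFS rate and DCR are too large for about 47 to 52 subjects to be fitted without penalisation; Firth's method is a cheap improvement

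*SAP*

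**What the plan says.** SAP version 4.0, section 7.2.4.3, plans subgroup results by background factor and then multivariable models. For the binary endpoints the text is: "using all background factors as explanatory variables, logistic regression analysis will be performed for PFS rate and DCR". For PFS, OS and TTF it is: "Using all background factors as explanatory variables, multivariate analysis will be performed using the Cox proportional hazard model".

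Seven factors are listed, each with two levels: age (split at 65), sex, ECOG performance status (0 or 1), primary tumour side, and then "adjuvant chemotherapy (yes, no), resection of primary lesion (yes, no), number of days since the start of first-line treatment", the last split at 600 days. One logistic model therefore has seven slopes and an intercept.

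The section names no variable selection, penalised or exact method, and no rule for non-convergence. SAP 7.2.4.5 sets 95% intervals and a two-sided 5% level for everything except the main analysis.

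On size, Protocol 6.2.2.2 says: "Taking into consideration of ineligible or discontinued subjects at approximately 10%, the target number of subjects was set to 52". The full analysis set (SAP 7.1) keeps only eligible subjects treated at the recommended dose, so 52 is the favourable case.

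**The concern.** Maximum-likelihood logistic regression needs enough subjects in the smaller outcome class for each coefficient. When there are few, estimates of real effects are pushed away from 1 and intervals become very wide. In some data sets a combination of factors predicts the outcome perfectly (separation), and no finite odds ratio exists. With seven factors and about 50 subjects, both models are in that range.

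What is at stake is the reliability of the adjusted odds ratios for the PFS rate and DCR. A factor with a moderate effect could be reported as a stronger one. If separation occurred, the analyst would have to choose a remedy after seeing the data.

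**Working it through.** **1. The plan's own sample size.** Protocol 6.2.2.2: "With the PFS threshold rate at 29%, PFS expected rate at 48% at 6 months from start of treatment", with "one-sided significant level at 5%, power at 80%, the necessary number of subjects will be 47". Exact binomial at N = 47: requiring at least 20 progression-free subjects gives P(X ≥ 20 | 0.29) = 0.033 and P(X ≥ 20 | 0.48) = 0.814. The figure of 47 reproduces. Adding 10% gives 47 × 1.1 = 51.7, so 52.

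**2. Subjects in the smaller class per factor.** The formula is N × min(p, 1 − p) / 7. The 48% is the design assumption. The DCRs of 44% (TAS-102 alone) and 72% (TAS-102 plus bevacizumab) are the background figures in Protocol 4.1.4.2. The 80% and 85% are assumptions.

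| Endpoint and rate | Smaller class, N = 52 | Per factor, N = 52 | Per factor, N = 47 |
|---|---|---|---|
| PFS rate 48% | 25.0 | 3.6 | 3.2 |
| DCR 44% | 22.9 | 3.3 | 3.0 |
| DCR 72% | 14.6 | 2.1 | 1.9 |
| DCR 80% | 10.4 | 1.5 | 1.3 |
| DCR 85% | 7.8 | 1.1 | 1.0 |

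**3. Simulation of the stated model.** N = 52, with 1,000 data sets per scenario and seven independent binary factors. The assumed prevalences were all 50%, mixed 25-50%, or skewed 15-45%. The true odds ratio was 1 or 2 per factor. Separation was tested by linear programming. Maximum-likelihood averages can be taken only over data sets with a finite estimate.

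*Bias, true odds ratio 2 (geometric means over the three prevalence patterns):*

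| Setting | Maximum likelihood | Excess over 2 | 95% upper / lower limit | Firth |
|---|---|---|---|---|
| PFS rate 48% | 2.32-2.42 | 16-21% | 17-23 | 2.01-2.05 |
| DCR 72% | 2.35-2.45 | 18-23% | 25-34 | 2.02-2.07 |

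A second, independent simulation gave about 2.3 and 2.5 (15% and 25% too high), against 1.99 and 2.11 with Firth. Firth lowered the root-mean-square error of the log odds ratio from 0.92 to 0.74 (PFS rate 48%) and from 1.07 to 0.88 (DCR 72%). Together the two simulations give the 15-25% range.

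*True odds ratio 1, PFS rate 48%:* the average estimate is 1.0, so there is no bias. However, 35-39% of the estimated odds ratios fall above 2 or below 0.5.

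*Share of data sets with no finite estimate (range over prevalence patterns and both odds ratios):*

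| Rate | Share |
|---|---|
| PFS rate 48% | 0-8% |
| DCR 44% | 0-11% |
| DCR 72% | 0-21% |
| DCR 80% (assumed) | 5-40% |
| DCR 85% (assumed) | 16-60% |

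The second simulation gave 5% at DCR 44% and 13.5% at 72%. With mixed prevalences and odds ratio 2, reducing N from 52 to 47 raises the share at DCR 72% from 8% to 10%.

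**4. Limits of these ranges.** They are not ceilings. Separation depends on factor prevalence, on correlation between factors, and on which level is favourable. Recoding the outcome turns a 29% rate into a 71% rate with every odds ratio inverted. The same simulation at 29% gave 0.5-35%, so a DCR near 72% could exceed 21% under a less favourable pattern of effects.

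**The case against.** **Is maximum likelihood actually stated?** No. The SAP says only logistic regression, and Firth's method would fit that wording. Maximum likelihood is an inference, though it is the usual meaning of the phrase when no other estimator is named. The objection stands as to wording. It also shows that the remedy contradicts nothing in the SAP.

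**Does the DCR model often have no finite estimate?** A reader might infer this, but the documents do not support it. They give no expected DCR for this combination. At the two benchmarks, most simulated data sets have finite estimates. One could derive a DCR from the design: with a constant hazard, 48% at 24 weeks implies 0.48^(8/24) = 78% progression-free at a first scan at week 8. That rests on an assumed hazard shape and ignores unevaluable subjects, who count as not controlled. It is still an assumption, lying between the 72% and 80% rows.

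**Are all the odds ratios inflated?** No. The bias concerns factors with a real effect. For the others the problem is imprecision.

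**Are these the only adjusted estimates of the factors?** No. The same section fits seven-factor Cox models for PFS, OS and TTF, and also plans results by subgroup. The logistic models are the only adjusted analyses stated for the PFS rate and DCR. No calculation here supports extending the criticism to the Cox models.

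**Does it matter?** The analysis sits under a subgroup heading, no decision depends on it, and intervals this wide already signal weakness. That limits the importance, but it is no reason to keep the weaker estimator.

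**Conclusion.** This holds as a cheap improvement. The two logistic models have about 3.6 (PFS rate 48%) and 2.1 (DCR 72%) smaller-class subjects per factor at N = 52, and fewer at 47. Fitted by standard maximum likelihood, they would overstate a true odds ratio of 2 by about 15-25%, with 95% upper limits 17 to 34 times the lower limits. There is a modest risk of no finite estimate at the documents' benchmark rates. That risk becomes substantial only if the DCR is about 80% or more, or if prevalences and effect directions are less favourable than those simulated.

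The conclusion rests on reading the text as maximum likelihood, on assumed prevalences and independence of the factors, and on a DCR the documents do not predict. The primary test of the 6-month PFS rate does not use these models.

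**What to change.** In SAP 7.2.4.3, state that the logistic models for PFS rate and DCR will be fitted with Firth's penalised likelihood, with profile penalised-likelihood 95% intervals and the same seven factors. Label the results exploratory. Leave the Cox sentence as it is.

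The cost is one sentence and a model option. Firth estimates are slightly shrunk. The intervals remain wide because seven factors are kept: the method removes most of the bias and the non-finite estimates, but it does not add information.
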